8.1.3 Statistical Analysis of PK Parameters

Descriptive statistics, including n, mean, standard deviation (SD), % coefficient of variation (CV), median, minimum, and maximum, will be calculated for each PK parameter determined from alpha₁-PI concentration data by the antigenic content assay. All PK parameters will be calculated using non-compartmental methods with WinNONLIN software (Pharsight Corporation, Cary, NC), which will be further described in the SAP.

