4.1 Study Design and Plan

GTI1401 study is a multi-center, open-label, trial to evaluate the safety and PK of weekly IV infusions of 60 mg/kg Alpha-1 MP in Japanese subjects with AATD. At least three adult subjects will be enrolled in the study. The study consists of an up to three-week Screening Period, and an eight-week open-label Treatment Period including a one-week PK Assessment Period after the last infusion. At the Week 9 visit when the PK evaluation period is completed, subjects will be asked whether they would like to participate in an extension trial (GTI1401-OLE). For subjects not intending to participate in the extension trial, the date of follow-up/study completion visit (30 days [4 weeks] after the last dose of the investigational drug) will be arranged. The total duration of study participation for subjects who complete the study will be up to 14 weeks.

After providing informed consent at the Screening Visit, subjects will be evaluated for study eligibility during the Screening Period (up to three weeks); for study inclusion and exclusion criteria. Eligible subjects will enter the eight-week Treatment Period to receive a total of eight weekly IV infusions of 60 mg/kg Alpha-1 MP; subjects will receive their first infusion of Alpha-1 MP at the Week 1 (Baseline) Visit. During the Treatment Period, weekly infusions of Alpha-1 MP will be performed at the study site during scheduled study visits at Weeks 1 (Baseline), 2, 3, 4, 5, 6, 7, and 8. Subjects will receive their last infusion of Alpha-1 MP at the Week 8 Visit and will then enter the one-week

PK Assessment Period. During the PK Assessment Period, subjects have a last PK blood sampling study visit at Week 9. A Follow-Up/Final Visit (30 days [4 weeks] post last study drug infusion) will occur for subjects who will not participate in Study GTI1401-OLE.

[figure not shown]
All subjects will have a blood sample collected at Weeks 1 (Baseline), 7, and 8 (prior to the infusion of Alpha-1 MP) and Week 9 which will be used for the measurement of trough alpha₁-PI levels.

Blood samples for PK parameters will be collected beginning at Week 8 and the collection of blood samples will extend into Week 9. The pre-infusion serial PK sample at Week 8 and the last serial PK sample (7 days after the Week 8 infusion) at Week 9 will also serve as trough blood samples for Weeks 8 and 9. The specific timing of all 10 serial blood samples includes:

- Immediately prior to infusion

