10.1.4 Figures of Concentration Versus Time Curves of All Subjects

Population	:	PK population
Contents	:	For all subjects combined, mean or median plasma alpha ₁ -PI concentration versus time curves following 8 weeks of treatments will be presented in one figure with the nominal time plotted on the x-axis.

All serum alpha₁-PI concentration vs. time curves will be plotted on both linear and semi-log scales.

A spaghetti plot (on the linear scale only) will be presented for all subjects following 8 weeks of treatment for concentration values vs nominal time.

Calculation of PK Parameters

The pharmacokinetic profiles of alpha₁-PI following weekly administration of Alpha-1 MP will be characterized by pharmacokinetic parameters, including area under the curve (AUC) at steady state following 8 weeks of weekly infusions (AUC_{0-7days}), maximum concentration (C_{max}), time to first observed maximum concentration (t_{max}), and half-life (t_{1/2}), based on alpha₁-PI concentrations in serum measured using content assay.

All PK parameters will be calculated using non-compartmental methods with WinNonlin software (Pharsight Corporation, Cary NC).

The pharmacokinetic parameters of interest are determined as follows:

- | | |
|------------------------|--|
| AUC _{0-7days} | area under the concentration vs. time curve at steady state over the weekly dosing interval (time 0 to 7 days), calculated by a combination of linear and logarithmic trapezoidal methods and expressed in the unit of concentration x time (mg·hr/dL). The linear trapezoidal method will be used for all incremental trapezoids arising from increasing concentrations and the logarithmic trapezoidal method will be used for those arising from decreasing concentrations. |
| C _{max} | the first observed peak serum alpha ₁ -PI concentration following drug infusion obtained directly from the experimental data without interpolation, expressed in concentration units (mg/dL). |
| t _{max} | the observed time to reach peak serum alpha ₁ -PI concentration obtained directly from the experimental data without interpolation, expressed in time units (hour). If there are more than one maximum observed concentration, the t _{max} is the time to the first observed peak concentration. |

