| t _{1/2} | the terminal half-life, calculated as (ln2)/K _{el} , expressed in time units (hour). The apparent terminal first-order elimination rate constant, determined by linear regression analysis of the natural log-linear segment of the plasma concentration-time curve, expressed in time ⁻¹ units (1/hour). At least 3 time points over 7 days following the treatment at week 8 will be included in the determination of K _{el} (Points prior to C _{max} or prior to the end of infusion are not used). |
| C _{min} | the observed serum concentrations prior to the start of infusions obtained at Weeks 7, 8 and at 7 days (168 hours) post infusion at Week 8, expressed in concentration units (mg/dL). |

Mean C_{\min} the average trough concentration at steady state, calculated as the mean value using the three C_{\min} measurements obtained at Weeks 7, 8 and at 7 days (168 hours) post infusion at Week 9.

Analysis of PK Parameters

For PK parameters descriptive statistics and geometric mean (except t_{\max}) will be calculated.

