10.1.5 Summary of PK Parameters		
Population	:	PK population
Contents	:	For following PK parameters, descriptive statistics including n, mean, standard deviation (SD), %CV, median, minimum, maximum and geometric mean (except t_{\max}) will be calculated. The digits to be displayed and units will be described in Table B. Data listing for PK parameter will be provided.

Table B

Contents	Digits to be displayed
AUC _{0-7days} [mg·hr/dL]	1 decimal place
C_{\max} [mg/dL]	2 decimal place
t_{\max} [hours]	2 decimal place
$t_{1/2}$ [hours]	2 decimal place

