 10.1 PK Analysis (GTI1401 only)
 10.1.5 Summary of PK Parameters

PK population

Parameter	Statistics	
AUC0-7days [mg · hr/dL]	N	xx
	Mean(S.D.)	xx x (xx x)
	%CV	xx x
	Median	xx x
	Min , Max	xx , xx
	Geometric mean	xx x
Cmax [mg/dL]	N	xx
	Mean(S.D.)	xx x (xx x)
	%CV	xx x
	Median	xx x
	Min , Max	xx , xx
	Geometric mean	
tmax [hours]	N	xx
	Mean(S.D.)	xx x (xx x)
	%CV	xx x
	Median	xx x
	Min , Max	xx , xx
t1/2 [hours]		xx
	Mean(S.D.)	xx x (xx x)
	%CV	xx x
	Median	xx x
	Min , Max	xx , xx
	Geometric mean	xx x

GTI 1401
 10 Exploratory Analysis

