10.1 PK Analysis (GTI1401 only)
10.1.9 Listing of PK Parameters

PK population

Subject Number	AUC0-7days [mg · hr/dL]	Cmax [mg/dL]	tmax [hours]	t1/2 [hours]	Cmin [mg/dL]
xxxx	xxxx	xxxx	xxx	xxx	xxx
xxxx	xxxx	xxxx	xxx	xxx	xxx
xxxx	xxxx	xxxx	xxx	xxx	xxx

>Sort order;
Subject Number

GTI 1401

10 Exploratory Analysis

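### The planned t1/2 is fitted to total alpha1-PI, so read as the half-life of the infused product it is too long; label the parameters as total and add a supplementary baseline-corrected t1/2

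*SAP*

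**What the plan says.** The subsection on calculating PK parameters, which follows SAP 10.1.4, bases AUC0-7days, Cmax, tmax and t1/2 on alpha1-PI "concentrations in serum measured using content assay". Protocol 8.1.3 likewise derives them from "concentration data by the antigenic content assay". Neither document describes a way to separate endogenous from infused protein.

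- **t1/2** is ln2/Kel, where Kel is "The apparent terminal first-order elimination rate constant, determined by linear regression analysis of the natural log-linear segment of the plasma concentration-time curve". At least three time points over the 7 days after the Week 8 infusion are used, none before Cmax or the end of infusion.
- **Cmax** is the first observed peak "concentration following drug infusion obtained directly from the experimental data without interpolation".
- **AUC0-7days** is a linear/logarithmic trapezoid on the measured concentrations.

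No subtraction is stated. SAP 10.1.5 then plans: "For following PK parameters, descriptive statistics including n, mean, standard deviation (SD), %CV, median, minimum, maximum" and a geometric mean (except for tmax). Table B and the layouts "10.1.5 Summary of PK Parameters" and "10.1.9 Listing of PK Parameters" say neither total nor corrected. The word total is attached to the trough objective (Protocol 3.2, SAP 3.2), not to these parameters.

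SAP 4.1 states: "All subjects will have a blood sample collected at Weeks 1 (Baseline), 7, and 8", before infusion. The Week 1 value has its own row in SAP 10.1.2 and is listed per subject. It is left out of mean Cmin and enters no PK parameter.

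**The concern.** The trial is titled and designed to study the pharmacokinetics of Alpha-1 MP, the product. Protocol 1.3 reports an elimination half-life for that product, and Protocol 4.3.3.3 uses half-life to justify weekly dosing. A reader will naturally take the t1/2 from this trial as a product property too.

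Patients with this deficiency still make some alpha1-PI. Protocol 1.1 gives 2.1 to 7.7 µM in S_iiyama homozygotes. The entry criterion sets only an upper limit (below 50 mg/dL), so no lower bound is documented. With that constant contribution left in, the log concentration curve is flatter than the decline of the infused protein, and t1/2 comes out longer. An unlabelled value could be mistaken for slow elimination in Japanese patients when part of it reflects the patients' own protein.

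**Working it through.** **Figures in the documents.** The SAP conversion reproduces: 10/44.3 = 0.2257, stated as 0.226; 50 mg/dL × 0.226 = 11.3 µM. Protocol 1.3: 146 h / 24 = 6.08 days, stated as 6 days. The documents give no expected t1/2 for this trial and no 60 mg/kg trough.

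**Direction.** Let C(t) = B + X(t), with B the constant endogenous level and X(t) the infused protein. The slope of ln C is X′/(B + X). While X falls, this is smaller in size than X′/X whenever B > 0. Every pairwise slope of ln C is therefore shallower, and so is the regression slope. This needs no numerical assumption beyond constant B.

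**Size: inputs.**
- True half-life 146 h (Protocol 1.3), assumed to be the infused product's own; k = ln2/146.
- Infused trough E at 60 mg/kg, assumed from the 27.7 µM mean trough at 120 mg/kg and dose proportionality (Protocol 1.3): E = (27.7 − B0)/2, where B0 is the assumed endogenous level in that earlier study. B0 = 2.1 gives 12.8, B0 = 5 gives 11.35, B0 = 7.7 gives 10.0 µM.
- Model: C(t) = B + E·exp(k(168 − t)); ln C regressed on t at 48, 120 and 168 h. The exponential factors are 1.7678, 1.2559 and 1. The mean time is 112 h, the deviations are −64, 8 and 56, and their sum of squares is 7296.

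**Example, B = 2.1, E = 11.35.** C = 22.164, 16.355, 13.450; ln C = 3.0985, 2.7945, 2.5990. Slope = (−64×3.0985 + 8×2.7945 + 56×2.5990)/7296 = −0.004167 per h. t1/2 = 0.6931/0.004167 = 166 h.

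**Example, B = 7.7, E = 11.35.** C = 27.764, 21.955, 19.050; ln C = 3.3237, 3.0890, 2.9471. Slope = −0.003149 per h. t1/2 = 220 h.

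| B (µM) | E = 12.8 | E = 11.35 | E = 10.0 | Excess over 146 h |
|---|---|---|---|---|
| 0.565 (2.5 mg/dL) | 150.9 | 151.5 | 152.2 | 3% to 4% |
| 1.0 | 154.6 | 155.7 | 157.0 | 6% to 8% |
| 2.1 | 164.0 | 166.3 | 169.1 | 12% to 16% |
| 5 | 188.8 | 194.3 | 200.7 | 29% to 38% |
| 7.7 | 211.8 | 220.1 | 230.1 | 45% to 58% |

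**Sensitivity.** Fixing the total trough at 27.7/2 = 13.85 µM instead gives 165.6 h at B = 2.1 and 282.3 h (+93%) at B = 7.7. Varying the true half-life over 72 to 146 h and E over 8.75 to 12.85 µM gives +9% to +66% over B = 2.1 to 7.7 µM.

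**What subtraction achieves.** I simulated 5% log-normal error on every sample, baseline included, with E = 11.35.
- The median of the three-subject mean t1/2 falls from about 169 h (all at 2.1 µM) and 225 h (all at 7.7 µM) to about 148 to 149 h.
- The median three-subject %CV falls from 19% to 14% when baselines are 2.1, 5 and 7.7 µM. Even then the corrected %CV is the higher one in about 27% of simulated trials. With equal baselines there is no gain: 12% against 12% at 2.1 µM, 14% against 14% at 5 µM.
- One subject's corrected t1/2 at B = 7.7 has a 95% range of about 106 to 231 h around 146 h.
- A 20% change in endogenous level between Week 1 and Week 8 moves the corrected value by about 3% at 2.1 µM and 10% at 7.7 µM.

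**The case against.** The best reply is that nothing in the plan is wrong. Both documents set out to describe alpha1-PI after dosing, the assay is named, the definitions show no subtraction, and the rate constant is already called apparent. With a minimum of three subjects, and with Week 1 and every Week 8–9 concentration listed, a reader can subtract by hand. SAP 1 also allows unplanned exploratory analyses. No test or decision depends on these parameters.

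Most of this stands, and it puts the point at the lowest severity. It does not remove the value of a pre-stated derivation: the choice of Kel points and the handling of prior therapy are better fixed before the values are seen.

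Three stronger readings are tempting and are not supported:
- **That AUC0-7days and Cmax are biased.** They are valid totals. The endogenous share is part of what they describe, and labelling them is editorial.
- **That correction will tighten the between-subject spread.** It helps only when baselines differ widely, and unreliably at n = 3.
- **That this trial's t1/2 can be set directly against 146 h.** That figure came from a functional activity assay and its correction status is not stated. If it was uncorrected, it is itself an apparent value (model: about 128 to 131 h true at 2 µM, 109 to 115 h at 5 µM), and corrected values beside it would look falsely short.

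The wording on values below the quantification limit in SAP 5.1, against the no-imputation sentence in SAP 10.1.2, is a separate question and adds no weight here.

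**Conclusion.** The point holds as a low-cost improvement, not as an error or a contradiction of the protocol. As a half-life of the infused product, the planned t1/2 is too long for any constant endogenous level above zero. That direction is firm. The sizes (about 12% to 16% at 2.1 µM, 45% to 58% at 7.7 µM, less at lower levels) are illustrative. They rest on an assumed 146 h true half-life, an assumed infused trough of 10.0 to 12.8 µM and single-exponential decline. The 2.1 to 7.7 µM range applies to S_iiyama homozygotes and may not describe everyone enrolled. Only the interpretation of an exploratory, descriptive parameter is affected; the safety objective, the total trough and the 11 µM comparison are not.

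**What to change.** In SAP 10.1.5, Table B and layouts 10.1.5 and 10.1.9:

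1. Keep t1/2, AUC0-7days and Cmax on total alpha1-PI as planned, and mark them as total, not baseline-corrected.
2. Add a supplementary baseline-corrected t1/2, after subtracting the subject's Week 1 pre-infusion value from each Week 8–9 concentration, with the same Kel time points as the total fit. A corrected AUC0-7days is optional, for description.
3. Do not compute corrected values when Week 1 is missing. Flag subjects whose records show recent prior alpha1-PI therapy: neither the exclusion criteria nor Protocol 4.5.1 lists a washout for it, so Week 1 may contain infused product and the subtraction would then overcorrect.
4. State with the table that corrected values assume constant endogenous production, that single-subject values are noisy, and that comparison with 146 h is conditional.

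Leave Cmin and the threshold count on total alpha1-PI. The cost is one further WinNonlin run, one or two table rows and label edits; no new samples are needed.

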10.1.5 Summary of PK Parameters		
Population	:	PK population
Contents	:	For following PK parameters, descriptive statistics including n, mean, standard deviation (SD), %CV, median, minimum, maximum and geometric mean (except t_{\max}) will be calculated. The digits to be displayed and units will be described in Table B. Data listing for PK parameter will be provided.

Table B

Contents	Digits to be displayed
AUC _{0-7days} [mg·hr/dL]	1 decimal place
C_{\max} [mg/dL]	2 decimal place
t_{\max} [hours]	2 decimal place
$t_{1/2}$ [hours]	2 decimal place

10.2 Lung density

Subjects will undergo CT scanning for diagnosis of clinically apparent pulmonary emphysema in GTI1401 study. This CT scan data will also serve as the baseline measurement of lung density for GTI1401-OLE study. Lung density collected by the CT scan data will be summarized in Demographics (parameter name=both).

In GTI1401-OLE study, the CT scan will be performed and summarized at Ext Week 52. The CT scan data will be accumulated for the future evaluation of lung density.

10.2.1 Summary Table of Lung Density		
Population	:	Safety population
Contents	:	For following parameters and locations, descriptive statistics including n, mean, standard deviation (SD), %CV, median, minimum and maximum will be calculated. The digits to be displayed, units and all location will be described in Table: Lung Density Parameter and Table: Target Location. Data listing for Lung density parameters will be provided.

Table: Lung Density Parameter

Contents	Conversion formula for analysis value	Digits to be displayed
Hu value 15 percentile [g/L]	Original value [housfield unit] + 1000	1 decimal place
Mean [g/L]	Original value [housfield unit] + 1000	1 decimal place
Standard deviation [g/L]	Original value [housfield unit] + 1000	1 decimal place
Percent below -856 hu [%]	Original value	1 decimal place
Percent below -910 hu [%]	Original value	1 decimal place
Percent below -950 hu [%]	Original value	1 decimal place
Total volume in cm ³ [mL]	Original value	1 decimal place
Air volume in cm ³ [mL]	Original value	1 decimal place

Table: Target Location

1	:	Lung
2	:	Lung, Left
3	:	Lung, Left Lower Lobe
4	:	Lung, Left Upper Lobe
5	:	Lung, Right
6	:	Lung, Right Lower Lobe
7	:	Lung, Right Middle Lobe
8	:	Lung, Right Upper Lobe
9	:	Lung, Thirds Left Lower
10	:	Lung, Thirds Left Middle
11	:	Lung, Thirds Left Upper
12	:	Lung, Thirds Right Lower
13	:	Lung, Thirds Right Middle
14	:	Lung, Thirds Right Upper

11 Safety Analysis

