 10.2 Lung Density Analysis (GTI1401 only)
 10.2.1 Summary Table of Lung Density

Safety population

Parameter [unit]	Location	Statistics	
		Median	xx x
		Min , Max	xx , xx
Mean [hounsfield unit]	LUNG	N	xx
		Mean(S.D.)	xx (xx x)
		Median	xx x
		Min , Max	xx , xx
....

All location for following parameters will be displayed after Air Volume in cm3;

- Mean [g/L]
- Standard deviation [g/L]
- Percent below -856 hu [%]
- Percent below -910 hu [%]
- Percent below -950 hu [%]
- Total volume in cm3 [mL]
- Air volume in cm3 [mL]
- Tissue volume in cm3 [mL]

GTI 1401
 10 Exploratory Analysis

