 10.2 Lung Density Analysis (GTI1401 only)
 10.2.2 Listing of Lung Density

Safety population

Subject Number	Location	Hu Value 15 Percentile [g/L]	Mean [g/L]	Standard deviation [g/L]	Percent below -856 hu [%]	Percent below -910 hu [%]	Percent below -950 hu [%]	Total volume in cm3 [mL]	Air volume in cm3 [mL]	Tissue volume in cm3 [mL]
xxxx	LUNG	xx x	xx x	xx.x	xx x	xx x	xx x	xx x	xx.x	xx x
	LUNG, LEFT	xx x	xx x	xx.x	xx x	xx x	xx x	xx x	xx.x	xx x
	LUNG, LEFT LOWER LOBE	xx x	xx x	xx.x	xx x	xx x	xx x	xx x	xx.x	xx x
	LUNG, LEFT UPPER LOBE	xx x	xx x	xx.x	xx x	xx x	xx x	xx x	xx.x	xx x
	LUNG, RIGHT	xx x	xx x	xx.x	xx x	xx x	xx x	xx x	xx.x	xx x
	LUNG, RIGHT LOWER LOBE	xx x	xx x	xx.x	xx x	xx x	xx x	xx x	xx.x	xx x
	LUNG, RIGHT MIDDLE LOBE	xx x	xx x	xx.x	xx x	xx x	xx x	xx x	xx.x	xx x
	LUNG, RIGHT UPPER LOBE	xx x	xx x	xx.x	xx x	xx x	xx x	xx x	xx.x	xx x
	LUNG, THIRDS LEFT LOWER	xx x	xx x	xx.x	xx x	xx x	xx x	xx x	xx.x	xx x
	LUNG, THIRDS LEFT MIDDLE	xx x	xx x	xx.x	xx x	xx x	xx x	xx x	xx.x	xx x
	LUNG, THIRDS LEFT UPPER	xx x	xx x	xx.x	xx x	xx x	xx x	xx x	xx.x	xx x
	LUNG, THIRDS RIGHT LOWER	xx x	xx x	xx.x	xx x	xx x	xx x	xx x	xx.x	xx x
	LUNG, THIRDS RIGHT MIDDLE	xx x	xx x	xx.x	xx x	xx x	xx x	xx x	xx.x	xx x
	LUNG, THIRDS RIGHT UPPER	xx x	xx x	xx.x	xx x	xx x	xx x	xx x	xx.x	xx x
xxxx	LUNG	xx x	xx x	xx.x	xx x	xx x	xx x	xx x	xx.x	xx x

>Sort order;
 Subject Number, Location

GTI 1401
 11 Safety Analysis

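### The SAP adds 1000 to the CT lung-density standard deviation, so every value of that parameter will be 1000 g/L too large

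*SAP*

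**What the plan says.** SAP section 10.2.1 contains a table of lung-density parameters with a conversion formula for each row. Three rows carry "Original value [housfield unit] + 1000": the 15th percentile, the mean and the standard deviation, all labelled in g/L. The rows for percentage below a threshold and for volumes use the original value unchanged.

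The standard deviation here is a parameter in its own right, with its own unit and number of decimals. It describes the spread of density within a lung region of one scan. It should not be confused with the between-subject SD that the same section requests as a summary statistic: "descriptive statistics including n, mean, standard deviation (SD), %CV, median, minimum and maximum will be calculated". The section names 14 target locations and adds: "Data listing for Lung density parameters will be provided".

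The layout plan carries the parameter through. The note to Table 10.2.1 reads "All location for following parameters will be displayed after Air Volume in cm3" and includes the standard deviation in g/L in its list. Listing 10.2.2 gives it a column next to the mean. No other section of the SAP or the protocol exempts this row or gives it a different formula.

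On the use of the scans, SAP section 10.2 says: "This CT scan data will also serve as the baseline measurement of lung density for GTI1401-OLE study".

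**The concern.** Adding 1000 moves the zero of the scale from water to air, and one HU then corresponds to one g/L. That is the correct step for any value that marks a position on the scale, such as a mean or a percentile. A standard deviation is built from distances between values, and distances do not change when the origin moves. Applying the offset to it yields a number that is not the SD of anything.

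The wrong values would stand in the GTI1401 summary table and in the subject listing. They would also stand in any extension-study output that reuses the derivation, since the GTI1401 scan is its baseline. SAP section 1 intends these analyses for regulatory submissions and manuscripts.

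**Working it through.** **Inputs**

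- Conversion for all three rows: HU value + 1000 (SAP 10.2.1).
- Target locations: 14 (SAP 10.2.1).
- Sample size: at least 3 subjects (SAP 5.4).
- Lung-density SD in HU: not given. Values of 50 to 200 HU are assumed below for illustration. The size of the error does not depend on them.

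**Algebra.** Let X be a voxel value in HU and Y = X + 1000 the same voxel in g/L.

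- mean(Y) = mean(X) + 1000, so the formula is right for the mean.
- P15(Y) = P15(X) + 1000, so it is right for the 15th percentile.
- SD(Y) = √E[(Y − mean(Y))²] = √E[(X − mean(X))²] = SD(X), because the two 1000s cancel. The SAP formula gives SD(X) + 1000, an excess of exactly 1000 g/L.

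**Numerical check.** Voxel distributions were simulated (400,000 normal draws each). The statistic of the converted voxels was compared with the SAP formula applied to the HU statistic.

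| Assumed mean, SD (HU) | P15: formula / true | Mean: formula / true | SD: formula / true | SD excess |
|---|---|---|---|---|
| −900, 50 | 48.19 / 48.19 | 99.86 / 99.86 | 1049.91 / 49.91 | 1000 |
| −880, 100 | 16.50 / 16.50 | 120.09 / 120.09 | 1099.92 / 99.92 | 1000 |
| −850, 150 | −5.41 / −5.41 | 150.14 / 150.14 | 1149.84 / 149.84 | 1000 |
| −850, 200 | −55.92 / −55.92 | 150.42 / 150.42 | 1199.54 / 199.54 | 1000 |

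The formula reproduces both location measures in every scenario and misses the SD by 1000 g/L in every scenario.

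**Relative size, under assumed SDs.** 60 HU becomes 1060 g/L (1060/60 = 17.7 times the true value); 100 becomes 1100 (11 times); 150 becomes 1150 (7.7 times).

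**Plausibility.** An SD cannot be negative, so the formula never prints less than 1000 g/L. Values confined to an interval cannot have an SD above half its width. If lung voxels lie between 0 and 1000 g/L (an assumption), the ceiling is 500 g/L. Even for 0 to 2000 g/L it is 1000 g/L.

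**Effect on the summary table.** Take three subjects with assumed lung SDs of 80, 100 and 120 g/L.

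| Statistic | Correct | By the SAP formula |
|---|---|---|
| Mean | 100 | 1100 |
| Median | 100 | 1100 |
| Minimum, maximum | 80, 120 | 1080, 1120 |
| Between-subject SD | 20 | 20 |
| %CV | 20/100 = 20% | 20/1100 = 1.8% |

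**Reach.** With 3 subjects and 14 locations, 3 × 14 = 42 listed values are wrong.

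**The case against.** The algebra cannot be disputed, so the best case against the point concerns its consequences.

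- **Only one parameter is affected.** The between-subject SDs printed for every parameter are untouched, because a constant cancels. This stands, and the point is limited accordingly.
- **The distorted %CV may never be printed.** The text of section 10.2.1 requests %CV, but the layout shell for that table shows only N, mean (SD), median, minimum and maximum. This stands too: the %CV consequence holds only if the text is followed rather than the shell.
- **The extension study loses little.** If the same formula were applied at Ext Week 52, the constant would cancel in a change from baseline, and subtracting 1000 recovers the original value. This is correct. The harm is to the reported levels; no information is lost.
- **The parameter is peripheral.** The demographics table uses only the 15th percentile and mean density, both converted correctly. The CT standard deviation is not a protocol objective or endpoint, and nothing on safety, trough level or pharmacokinetics depends on it. This limits the importance of the error but does not make the number right.
- **The programmer or a reviewer would notice.** Possibly, since the listing puts the mean and the SD side by side. But the SAP is the specification, and a correct program would have to depart from it.

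One circumstance would rescue the formula: source SDs stored with 1000 already subtracted. Nothing in the documents suggests this, and the table describes its input as the original value in Hounsfield units.

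**Conclusion.** The conversion is wrong as written for the standard deviation row and right for the 15th percentile and the mean. Each listed value of the lung-density SD parameter, and its mean, median, minimum and maximum, will be 1000 g/L too large. That figure is an identity and rests on no assumption about the data. The ratios (7.7 to 17.7 times for an SD of 60 to 150 HU) and the %CV example (1.8% instead of 20%) rest on assumed values and serve only as illustration. The error corrupts a reported number, but in a descriptive, exploratory table that supports no other conclusion of the trial.

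**What to change.** In the parameter table of SAP section 10.2.1, change the formula in the standard deviation row to the original value without an offset, as already used for the percentage and volume rows. The g/L unit can stay, because one HU equals one g/L on this scale. Keep the +1000 for the 15th percentile and the mean. Use the corrected derivation for Table 10.2.1, Listing 10.2.2 and any Ext Week 52 output of the extension study.

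Two inconsistencies can be settled in the same edit. The layout shell labels the mean in Hounsfield units while its own note and the SAP table say g/L. The shell also omits the %CV that the text requests.

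The cost is one table cell and one line of the program, plus the shell edits. No new data are needed, and outputs already produced can be corrected by subtracting 1000 from the values of this parameter and recalculating its %CV.
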